16 fractions is a common course of breast RT). For the second group, we will reverse the order, using MixRT for fractions 1-5 and 3-point alignment for fractions 6-10. In this way, each patient will serve as their own control. In all cases, patient alignment will be verified using CBCT which will be registered to the simulation CT by the treatment therapists using the standard clinical workflow. The magnitude of the resulting shift will be recorded. If further adjustment is necessary, the number of repeated CBCTs will be recorded along with the shift magnitude. All registrations will be reviewed by a board-certified radiation oncologist (one of the co-investigators) who will qualitatively assess the accuracy of the setup while blinded to the setup method. The process for mixed-reality alignment is noted below:

1. Identify the patient and initialize their hologram by detecting a QR-coded cube attached to the treatment device.
2. Setup the patient according to their setup photos, related immobilization devices (typically only an inclined breast board), and 3-point alignment. Further match the patient to their hologram as viewed through the HoloLens 2 device.
3. Utilize IGRT to verify proper alignment per protocol or departmental standards.
4. Make corrections as needed based on IGRT.
5. Repeat steps 1-3 if necessary.

For patients receiving proton therapy, setup typically includes routine CBCT, the challenges of which were previously discussed for non-rigid alignment including prolonged setup time and increased imaging dose. The primary goal of this sub-aim is thus to show that MixRT can reduce setup time and the amount of imaging dose in cases requiring CBCT alignment. To evaluate this, we will recruit an additional 12 patients scheduled to receive RT using a supine, pencil-beam scanning approach. As with 3DCRT/IMRT approach, we will divide patients into two groups using an alternating method and alternate the setup approach between fractions 1-5 and 6-10, reversing the order between the two groups. Setup time will be tracked from the moment the patient lies on the treatment couch to when the final position is confirmed by the therapist prior to treatment. Patient alignment will be verified/quantified in a similar manner as noted above.

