A window period of 2 additional fractions is permissible for the collection of study data. This window period is provided to allow a patient to remain on study through her 12th fraction of treatment if the patient is not able to receive the study intervention during one to two of her first 10 fractions.

To summarize, we intend to enroll 12 patients receiving either 3DCRT or IMRT and 12 patients receiving proton therapy. Within each modality, patients will be randomized into two groups using an alternating method. The order in which MixRT will be utilized will be reversed between the groups. The measured data will include registration accuracy (6 DoF shifts), setup time, and number of CBCT's utilized. Registration accuracy will be quantified using the image registration module that is used as part of the IGRT process. Setup time will be quantified using a stopwatch.

The number of CBCT's will be quantified via counting the number that are used during the setup process. Patients receiving photon IMRT receive daily CBCT as part of the standard of care. Thus, this investigation would likely not introduce additional imaging dose for these patients. For proton therapy CBCT is used weekly, and for 3DCRT it is not routinely used. Thus, this investigation would represent a marginal increase in the utilization of CBCT for these patients, up to 10 extra CBCT's nominally.

Setup during Verification CT

Radiotherapy patients at UFHPTI often receive repeat CT scans (verification scans) at periodic timepoints during the course of treatment to assess for anthropomorphic changes that could have dosimetric effect. Reproducing the posture from the initial CT simulation is critically important yet difficult to achieve due to the lack of real-time feedback. For patients who receive a verification CT (likely all proton patients), we will implement holographic alignment during this process and assess its accuracy in comparison to CT acquisition without the aid of holographic alignment. The procedure will be as follows:

1. Identify enrolled patients scheduled to receive a verification CT scan.
2. Setup patient without the aid of holographic alignment (standard method).
3. Acquire verification CT scan.
4. Dismantle the setup.
5. Utilize holographic alignment to correct patient posture. This involves a therapist wearing the HoloLens 2 device and viewing the patient's reference hologram overlaid the patient. The therapist will manually adjust the patient to match the hologram.

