- **Describe how subjects protected health information will be accessed and by whom:** Data will be accessed and collected from the treatment planning system, RayStation, clinical database software, MimVista, and the radiation oncology information system, Mosaiq. These are all clinical systems used to facilitate patient treatment at UFHPTI. Only the investigators and research staff will screen or access patient medical records for the purpose of this study.
- **Describe how consent will be obtained, by whom, and in what setting, and how and where consent will be documented:** Patients will be consented during standard of care clinic visits by protocol/consent trained staff. Documentation of informed consent will be noted in the patient's chart in Mosaiq.
- **Describe the number of subjects that will be screened, and the number of evaluable subjects needed based on power analysis:** Up to 40 patients may enroll, but approximately 24 patients are needed in this pilot study. We recognize the study is underpowered, however, this is a pilot study where the purpose is to collect preliminary data to help establish viability of the method.
- **Describe completely all drugs, devices, or instruments that are being proposed:** This study involves no drugs. The specific device, HoloLens 2, will be worn by the therapists during patient setup. This device will display relevant information needed during the setup procedure including setup photos and the patient's hologram as registered to the radiotherapy device. Final positioning will be made according to IGRT which is standard of care.
- **Provide a clear and concise description of the treatment, intervention, or observation to be carried out in the study:** The intervention for the study is the use of the HoloLens v2 device to aid in patient alignment. As noted in the study

description above, this device utilizes mixed-reality to display a hologram of the patient as registered to the treatment machine. The patient will be matched to the hologram by a radiation therapist who is wearing the device. The patient will not wear the device. The device will not come into contact with the patient. The sensors on the device emit only non-ionizing signals such as IR.

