- **Clearly state the nature of the experimental control (placebo, other treatment, historical) or the absence of a control:** Patients who receive verification CT, each patient will have their own control represented by the verification CT acquired without the use of holographic alignment. During the use of MixRT during patient setup, each patient will also have their own control represented by the sub-set of fractions where data is collected but holographic alignment is not employed.
- **Describe any randomization procedures:** Randomization is included during the use of MixRT guided patient setup where the patients are segmented into two groups. The order in which holographic alignment is introduced into the course of treatment is reversed for the two groups. The purpose is to control for setup variation which typically decreases after the first few fractions of treatment.
- **Describe completely all physical examinations, blood tests, x-rays, any special tests or procedures, surveys, questionnaires, and/or observations that will be used to obtain information about subjects:** No additional tests will be done that are outside the radiotherapy workflow. The study does include an increased utilization of specific aspects of the radiotherapy workflow, namely addition CT and CBCT acquisition.
- **Describe who will be responsible for obtaining the information and in what type of setting the information will be obtained:** Data will be collected during the course of radiotherapy treatment and during the acquisition of verification CT scans. Either the study investigators or trained radiation therapist will be responsible for collecting this data. The PI will serve as the primary data manager based on familiarity with the data.
- **Describe how these activities will answer the study questions:** The main question we seek to answer is whether mixed reality visualization is a feasible method for patient alignment in radiation therapy. To answer this question, we will collect relevant clinical data including registration error, registration time, and the amount of imaging used during the registration process. While we are not yet attaching power or a formal sample size structure to this data, we believe this data work together as our primary endpoints to answer the question of feasibility.

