- **Discuss why the risks to subjects are reasonable in relation to the anticipated benefits and in relation to the importance of the knowledge that may reasonably be gained:** We believe the marginal increase in risk of developing a radiation induced malignancy incurred through participation in this study is low. The immediate benefit to the study participants is that the additional CT and CBCT may improve the accuracy of their setups for instances in which these images are acquired. The long-term benefit for patients outside the study cohort will be the knowledge gained about the clinical use of mixed-reality for patient setup. We believe this method can improve the patient setup and alignment process and will eventually make the process faster and with the use of less ionizing radiation.

10.) Possible Benefits:

- **Describe the potential benefits to subjects or to others that may be reasonably expected to result from the research:** Based on prior study utilizing anthropomorphic phantoms, we anticipate that our patient alignment system will ultimately reduce setup time and the number of X-ray images used for alignment. By reducing setup time, we increase patient comfort and minimize the risk of patient movement during treatment. By reducing the number of X-ray images used, we reduce the amount of ionizing radiation the patient receives.
- **If there is no potential for direct benefits, you must state this in the Informed Consent Form:** Due to the fact that CBCT will be utilized for all study fractions, patients may benefit from a more accurate setup if CBCT was not standard of care for their treatment approach.
- **Will the research study benefit future populations?** Yes, possibly.

11.) Conflict of Interest:

- **Describe any real or potential conflict of interest you or any other investigators may have with regard to this research project:** The principal investigator has filed a provisional patent application in coordination with UF Innovate related to concept of aligning a patient via hologram.
- **When deciding whether a conflict may exist, consider the following:**
 - **Do you, the University of Florida, or any of the sub-investigators hold a patent or license for any material, object, or process used in this project?** No
 - **Is a patent or license pending or under consideration or is there any intention to file a patent application at a later date?** Yes.

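### Setup time, a joint primary endpoint, is taken by stopwatch by staff who see the setup method and may include the investigator with a patent application on it; a recorder without that interest would cost little.

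*Combined protocol and SAP*

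**What the plan says.** Under 6.) Research Plan, the item on how the activities answer the study questions lists registration error, registration time and amount of imaging, and adds: "we believe this data work together as our primary endpoints to answer the question of feasibility". The proton paragraph of the mixed-reality setup section makes shorter setup time and less imaging dose the primary goal of that sub-aim.

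The three endpoints are measured differently. The summary of that section takes registration accuracy from the image registration module used in the IGRT process. For time it says "Setup time will be quantified using a stopwatch", and for imaging "The number of CBCT's will be quantified via counting the number that are used during the setup process". The timed interval is defined in the proton paragraph only: "Setup time will be tracked from the moment the patient lies on the treatment couch to when the final position is confirmed by the therapist".

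On who records, the Research Plan says "Either the study investigators or trained radiation therapist will be responsible for collecting this data", and it names the principal investigator as primary data manager. The confidentiality item puts setup times, shifts and CBCT numbers in a spreadsheet on computers that the investigators control. Section 11.) Conflict of Interest states: "The principal investigator has filed a provisional patent application", on the concept of aligning a patient via hologram. The same section answers No on holding a patent or license and Yes on one pending or planned.

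The only blinding in the plan is that of the radiation oncologist who reviews registrations qualitatively.

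**The concern.** Setup time is the outcome nearest to the claim that the method is faster, and its measurement is the least protected of the three. Both ends of the interval are human calls: when the patient counts as lying on the couch, and when position is confirmed. The person with the stopwatch can see whether a therapist wears the headset. The plan allows that person to be an investigator, and the investigator with the declared interest manages the data. No independent timer, blinded recorder or check against source data is described for time or CBCT count.

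Two things are at stake. A small, consistent difference in when the watch is started or stopped would enter the estimate carried forward to the larger studies and eventual FDA clearance named in the Specific Aims. In addition, section 9.) Possible Discomforts and Risks ends holographic alignment for a patient when setup time rises by more than 30% in two consecutive sessions. The same reading may therefore also affect which fractions receive MixRT.

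**Working it through.** The plan gives no SD, effect size or power for setup time, so it has no figure to reproduce beyond the sample size, 12 + 12 = 24, which agrees with its stated total.

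**Why the crossover does not remove the bias.** Let Δ be the true MixRT-minus-standard difference, p1 and p2 the period effects (fractions 1–5 and 6–10), and b a recording bias tied to the method. The expected paired difference is:

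- standard first: Δ + b + (p2 − p1)
- MixRT first: Δ + b + (p1 − p2)

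With equal groups, the average is Δ + b. The period effect cancels and b does not.

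**How much b could matter.** Inputs from the plan: n = 12 per modality and a 95% interval for the paired difference. Assumed: one paired difference per patient, Δ = 0, SD of the paired differences 1.5 to 3 min, b = 0.25 to 1 min. The probability that the interval excludes zero is P(|T| > 2.201), where T is non-central t with 11 df and non-centrality b√12/SD.

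| b (min) | SD 1.5 | SD 2 | SD 3 |
|---|---|---|---|
| 0 | 5.0% | 5.0% | 5.0% |
| 0.25 | 8.3% | 6.8% | 5.8% |
| 0.5 | 18.4% | 12.4% | 8.3% |
| 1 | 55.8% | 35.3% | 18.4% |

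For example, b = 0.5 and SD = 2 give non-centrality 0.5 × 3.464 / 2 = 0.866 and probability 12.4%. The interval's half-width at SD 2 is 2.201 × 2 / 3.464 = 1.27 min.

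**Against the plan's own reference value.** Section 7.) Statistical Analysis compares the mean paired difference in time with 5 minutes. The table uses zero, so it describes the promised confidence interval and not that test. The shift is the same in either case, because the estimate moves by b whatever value it is compared with.

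**The discontinuation threshold.** The Background cites a study in which setup time fell from 11 to 6 minutes. If times here were similar (an assumption), a 30% rise would be 0.3 × 11 = 3.3 min or 0.3 × 6 = 1.8 min. A 0.5 min recording difference would be 0.5/3.3 = 15% or 0.5/1.8 = 28% of that margin.

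**CBCT count.** Each method has 12 × 5 = 60 fractions per modality, each with a CBCT. If 10% to 30% of fractions needed one repeat (an assumption), the total would be 66 to 78 scans. One miscounted scan is then 1/66 = 1.5% to 1/78 = 1.3% of the total.

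**The case against.** The strongest reply is that this is an openly underpowered pilot and that staff cannot be blinded to a headset. The patent application is disclosed, a study statistician takes part in the analysis, and an institutional committee monitors annually. All of that is true and it limits the severity. However, none of it checks a stopwatch reading against anything, and a small sample makes an estimate imprecise without excusing avoidable bias.

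A second reply is that bias and SD are both invented. That also stands: a bias of 0.25 min at SD 2 gives only 6.8% against a nominal 5%. The table shows sensitivity and is not evidence that bias occurs.

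A reader might infer more than the documents support:

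- That the investigator holds a patent. Section 11 answers No; a provisional application has been filed.
- That CBCTs are tallied by hand. The plan says they are counted and names no source, so counting stored scans fits its wording.
- That a miscount would matter greatly and be undetectable. The outcome is scans used, not repeats alone, and each scan is a discrete event that can be verified.
- That stored records could replace most of the timing. The Research Plan draws data from RayStation, MimVista and "the radiation oncology information system, Mosaiq", but does not say that any of them logs setup events. The moment of lying down on the couch may not be captured at all.

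**Conclusion.** The point holds for setup time, as an avoidable weakness in measurement that is cheap to reduce. It does not show that any figure in the plan is wrong or that any recorder would favour a method. Its size cannot be derived from the documents. Under the stated assumptions (12 patients, no true difference, SD 1.5 to 3 min), the chance that the interval excludes zero rises from 5% to 6–8%, 8–18% or 18–56% for a bias of 0.25, 0.5 or 1 min. The CBCT count is a minor limb. For that endpoint, the choice by unblinded therapists to repeat a scan and the subjective assessment planned in section 7 matter more than who counts.

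**What to change.** Amend the summary of the mixed-reality setup section and the item on who collects the data, as follows.

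1. A treating therapist, already a permitted recorder, notes start and stop as times of day, to the second, in both methods and both modalities. The start and stop are those in the proton paragraph.
2. Investigators with an interest in the patent application do not time setups or enter outcome data.
3. Where the clinical systems log CBCT acquisition and registration acceptance (to be confirmed, since the documents do not say so), the CBCT count per fraction comes from the stored image record. The logged acceptance time serves as the stop or as a cross-check on it, chosen before enrolment and applied alike to both methods.

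Beam-on should not replace the defined stop ("to when the final position is confirmed by the therapist prior to treatment"). It would change the endpoint, and nothing in the documents shows that the added interval is equal between methods.

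The cost is protocol wording, slightly more recording work and a data export, with no extra imaging. Therapists remain unblinded. The change reduces bias in recording but does not remove bias in when a position is accepted or a CBCT repeated.

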- **Describe the inclusion and exclusion criteria for this project:** This study will target adult patients who are planning to undergo photon or proton radiation therapy at UFHPTI for treatment of the breast or chest wall. As this type of treatment is rare in men, the study will focus on female patients only.
- **Provide a thorough step-by-step description of what you intend to do throughout the course of the study in a logical and sequential format:**

Hologram creation

For all patients included in this study, we will create holograms based on the external body contour derived from their planning CT dataset. This contour is routinely segmented during treatment planning; thus, we will only need to access the existing contour located in the software system MimVista and export it to our software system. We will also access patient setup photos located in a clinical file system and export these to our application.

Mixed-reality guided patient setup

At UFHPTI, we treat breast/chest wall patients using various modalities and techniques. In all cases, patient setup begins with a 3-point alignment. The additional use of IGRT depends on modality, approach, and patient-specific variables. Most patients treated with 3D conformal photon therapy (3DCRT) receive only weekly IGRT, including kV orthogonal and MV portal imaging. The 3-point alignment, thus, represents the standard setup for the majority of treatment, both here and across the nation, as 3DCRT is the most common technique for breast RT. As such, one of our primary aims is to pilot the clinical implementation of MixRT with the goal of accuracy similar to or better than a traditional breast setup involving 3-point alignment (5mm tolerance).

We will recruit 12 patients scheduled to receive whole breast or chest wall RT using a supine, 3DCRT or IMRT approach. All patients will be consented for a study comparing the accuracy of MixRT with a traditional 3-point alignment as quantified using CBCT. To control for setup variation which typically decreases after the first few treatment fractions, we will stratify patients into two groups using an alternating method. In the first group, the therapists will position the patient using 3-point alignment during fractions 1-5 (5 total), then using MixRT for fractions 6-10 (note:

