- **Briefly outline the data analyses that are proposed and who will do the analysis:** Mean estimates and associated 95% confidence intervals will be attained for registration error and registration time for the mixed reality and standard of care methods and the paired difference of the two techniques. We will assess feasibility using a paired T-test. The hypothesis is that the mean paired differences across all measures of registration error and registration time are not significantly different than 3 mm and 5 minutes, respectively. The number of CBCTs collected as part of the registration process will be assessed subjectively since count data are not truly continuous. This analysis will be carried out by the study investigator and study statistician.
- **Describe your plan for conducting interim analysis. What stopping rules are in place?** N/A.

8.) Data Safety and Monitoring Plan:

- **Is there a Data Safety Monitoring Board (DSMB) or an oversight committee for this research project?** The UF Data Integrity & Safety Committee will provide oversight through annual monitoring.

- **Describe your plans for monitoring study conduct and subject safety:** The Principal Investigator will be responsible for monitoring.
- **Provide Information about the DSMB or committee including who is on the committee, how frequently will the committee meet, and when will you get information from the committee:** N/A

9.) Possible Discomforts and Risks:

- **Identify all discomforts and risks (physical, psychological, social, and/or economic) study participants may encounter, listing more common risks first and less common risks separately:** Based on prior study utilizing anthropomorphic phantoms, we anticipate that our patient alignment system will ultimately reduce setup time and the number of X-ray images used for alignment. We have yet to try this with patients, however, and there is a risk that it could marginally increase setup time, at least during the initial implementation.

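### The paired t-test leaves out the order groups that were set up to control the early-fraction effect, so any such effect is counted as random scatter

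*Combined protocol and SAP*

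**What the plan says.** Section 6 (Research Plan, Mixed-reality guided patient setup) gives the reason for the two groups: "To control for setup variation which typically decreases after the first few treatment fractions, we will stratify patients into two groups". One photon group has 3-point alignment first and MixRT second; the other is reversed, "using MixRT for fractions 1-5 and 3-point alignment for fractions 6-10". The proton cohort follows the same scheme: "alternate the setup approach between fractions 1-5 and 6-10, reversing the order between the two groups". The paragraph on randomization repeats the aim: "The purpose is to control for setup variation which typically decreases after the first few fractions of treatment". Allocation alternates within each modality, with 12 photon and 12 proton patients planned, so about 6 per order group.

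The outcomes are described in two ways. For the CBCT check, "The magnitude of the resulting shift will be recorded"; in the summary, "The measured data will include registration accuracy (6 DoF shifts), setup time" and the number of CBCTs.

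Section 7 plans means and 95% confidence intervals for each method and for the paired difference, then: "We will assess feasibility using a paired T-test". The hypothesis is that the mean paired differences do not differ significantly from 3 mm and 5 minutes. Section 7 contains no order or period term, no summary by order group, and no statement of whether the pair is a patient or a fraction. Section 6 does say that each patient serves as her own control, which points to the patient.

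**The concern.** The protocol names a nuisance effect, designs against it, and then does not use that design feature in the analysis. In a two-period reversal, an early-fraction effect enters the MixRT-minus-standard difference with a plus sign in the group that has MixRT first and a minus sign in the other. A plain paired t-test treats that systematic gap between the groups as patient-to-patient noise.

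Two things are at stake. The first is precision, in a pilot meant to supply estimates for larger studies. The second is the feasibility conclusion. Because the hoped-for result is a non-significant test, anything that inflates the standard error makes that result easier to obtain. A third, conditional, risk is a shifted mean if the order groups end up unequal in the analysis.

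**Working it through.** **Inputs from the documents.** 12 patients per modality; alternating allocation, hence n1 = n2 = 6; 95% intervals. Alpha is not stated; two-sided 0.05 is taken from the 95% intervals. The sample size was chosen for practicality, so there is no power figure to reproduce.

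**Assumed.** The documents give neither the period effect nor the SD. Let r be the period effect (mean of fractions 1-5 minus mean of fractions 6-10) divided by the patient-level SD of the difference. The range shown is 0 to 1.

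**Model.** With SD set to 1, a patient's MixRT-minus-standard difference has mean τ + r if MixRT comes first and τ − r if it comes second. This assumes one difference per patient, an early effect that moves the mean, and the same effect under both methods.

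**Formulas**, with n = n1 + n2:

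- Paired half-width (from the expected variance) = t(0.975, n−1) × √{[1 + r² × 4·n1·n2 / (n(n−1))] / n}
- Order-group half-width = t(0.975, n−2) × √(1/n1 + 1/n2) / 2
- Bias of the paired mean = r × (n1 − n2) / n

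**Six per group.** t(11) = 2.2010 and t(10) = 2.2281. The order-group half-width is 2.2281 × √(1/6 + 1/6) / 2 = 0.6432 at every r. In the paired variance, the multiplier of r² is 4 × 36 / (12 × 11) = 1.0909.

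| r | Variance factor | Paired half-width | Paired / order-group |
|---|---|---|---|
| 0 | 1.00 | 0.6354 | 0.988 |
| 0.25 | 1.07 | 0.6567 | 1.021 |
| 0.5 | 1.27 | 0.7168 | 1.114 |
| 1 | 2.09 | 0.9187 | 1.428 |

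The widths are equal where r² = [(2.2281/2.2010)² − 1] / 1.0909, that is r = 0.15.

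For scale at r = 0.5: if the SD were 2 mm, the half-widths would be 1.43 mm (paired) and 1.29 mm (order-group). If it were 5 minutes, they would be 3.58 and 3.22 minutes.

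**Coverage and power by simulation, 6:6.** Coverage of the nominal 95% paired interval is about 95.6%, 97.0% and 99.4% at r = 0.25, 0.5 and 1. The order-group interval stays at about 95%. If the true mean lies 1 SD from the tested value, the paired test detects this in 88%, 82% and 61% of trials at r = 0, 0.5 and 1. The order-group test stays at about 88%.

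**Unequal completion.** Starting from 6:6, loss gives 6:5 or 6:4. The paired mean then shifts by 1/11 = 0.09 or 2/10 = 0.20 of the period effect. The equally weighted order-group mean does not shift.

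**If the unit were the single fraction.** Treating 12 × 5 = 60 fraction pairs as independent, with an assumed within-patient correlation of 0.3, simulated coverage is 81% with no period effect and 86% at 0.5 single-fraction SD. The error then runs the other way.

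**The case against.** The strongest reply is that the design already does the work. Alternation gives about 6:6, the paired mean is then unbiased under the stated model, and what remains is some precision in a pilot that admits it is underpowered. This stands as far as it goes: a reader might infer that the planned estimate is invalid, and the documents do not support that.

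The size is also unknown. The protocol says that setup variation falls after the first few fractions; it does not say that the mean shifts. A shift in the mean is plausible for shift magnitude and setup time. Signed shifts would mainly change in variance. Averaging over five fractions dilutes an effect confined to the first few, and at 0.25 SD the loss is only 2%.

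The early effect may also belong to one method. Section 9 allows that MixRT could lengthen setup during initial implementation. If an early excess falls on one method only, the effective period term is halved: the paired interval is 0.4% narrower, 2% wider and 11% wider at an excess of 0.25, 0.5 and 1 SD. Both analyses then carry the same shift of half the excess, so the order-group analysis does not remove it.

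A reader might infer that the discontinuation rule in Section 9 will unbalance the groups. The documents do not support this. The rule stops use of the device; it does not say that the patient leaves the analysis, and "A window period of 2 additional fractions is permissible for the collection of study data". Unequal loss is possible, not predicted.

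Finally, a reader might take a wide interval as a cautious, harmless error. That fails on two counts: it holds only if the patient is the unit, which Section 7 does not state, and extra width favours the non-significant result that Section 7 hypothesises.

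**Conclusion.** The concern holds in a limited form. Section 7 should use the order groups, because reversing the order is the plan's stated protection against the early-fraction effect.

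At 6:6, with one difference per patient and a common early effect on the mean, omitting the order groups costs precision and does not bias the mean. The cost is negligible at 0.25 SD, moderate at 0.5 SD (11% wider) and large only at 1 SD (43% wider). Below about 0.15 SD the plain paired interval is slightly the narrower one. None of these effect sizes comes from the documents. The bias under unequal completion is conditional and modest: 0.09 to 0.20 of the period effect at 6:5 and 6:4.

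The point is still worth acting on because the loss of precision makes the hypothesised result easier to reach, because the unit of analysis is left open, and because the remedy uses data already collected. It should be amended, but it does not invalidate the trial.

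**What to change.** In Section 7, under the proposed data analyses:

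1. State that the patient is the unit of analysis.
2. Within each modality, and for each planned measure of registration error and setup time, form each patient's difference as her mean under MixRT minus her mean under the standard method.
3. Estimate the method effect as the equally weighted average of the two order groups' mean differences, using the pooled within-group SD and n − 2 degrees of freedom. Give the 95% interval and make the planned comparisons with 3 mm and 5 minutes on this basis.
4. Report the number of completers and the mean difference in each order group.

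The cost is a few sentences and no new data. With no period effect, the interval is 1.2% wider at 6:6 (0.6432/0.6354), about 2% wider at 6:5 (0.6849/0.6718) and 4.0% wider at 6:4 (0.7443/0.7154). With unequal groups and a small period effect, the gain is therefore removal of bias, not precision.

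The change does not deal with carry-over between methods, an early effect specific to one method, or the use of a non-significant test as evidence of feasibility. The last needs its own correction.
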